6.1.1 Dosage Form and Packaging

The 3 developmental products (serum, lotion and cream) will be supplied to the clinical site as labelled packaged pump packs or tubes in a kit for dispensing by the site staff.

The content of the product labels will be in accordance with all applicable regulatory requirements and will be the responsibility of the GSK CH Global Clinical Supplies group. Each study label will contain, but not be limited to, protocol number, container number, directions for use and storage requirements.

Care should be taken with the supplied products and their labels so that they are maintained in good condition. It is important that all labels remain intact and legible for the duration of the study. Subjects should be instructed to not remove or deface any part of the study label.

All products supplied are for use only in this clinical study and should not be used for any other purpose.

6.1.2 Preparation and Dispensing

The 3 developmental products (serum, lotion and cream) will be dispensed by suitable trained unblinded site personnel according to the randomization schedule provided.

These staff members will not be involved in any safety, efficacy assessments or other aspects of the study that could be influenced by the knowledge of product a subject has been assigned to use. An additional member of site staff should ensure the dispensing procedures are completed accurately.

Subjects will be centrally randomized to one of the 3 study arms using an Interactive Response Technology (IRT) in accordance with the randomization schedule generated by an approved GSK CH vendor, prior to the start of the study, using validated software.

6.2 Administration

Only subjects enrolled in the study may receive study products and only authorized site staff may supply study products. All study interventions must be stored in a secure, environmentally controlled, and monitored (manual or automated) area in accordance with the labeled storage conditions with access limited to the authorized site staff only.

The first application of the assigned product will be conducted by the subject under the supervision of a trained technician at the study site at Visit 2 (Baseline) following completion of the baseline dermatologist and ophthalmologist assessments and subject self-assessment questions.

If Visit 1 and Visit 2 are combined, first application of the assigned product will be conducted by the subject under the supervision of a trained technician at the site following completion of the baseline dermatologist and ophthalmologist assessments and subject self-assessment questions. There should be a minimum of 30 minutes after the LAST has completed before the baseline product application.

Subjects will be instructed to self-administer their assigned product per the usage instructions the same evening of the visit and continue to use for a total of 21 days (+2 days).

6.2.1 Dosing Errors

Dosing errors may result, in this study, from the administration of:

- the wrong product,
- at the wrong amount,
- by the wrong subject,
- at the wrong time,

Such dosing errors occurring to a study subject are to be captured in the CRF.

Dosing errors are reportable irrespective of the presence of an associated AE, including:

- Dosing errors involving subject exposure to any of the study products;
- Potential dosing errors or uses outside of what is foreseen in the protocol that do or do not involve the participating subject.

If a dosing error is accompanied by an AE, as determined by the investigator, the dosing error and, any associated adverse event(s) are to be captured in the CRF AE form.

Such medication/dosing errors occurring to a study subject are to be captured in the CRF. In the event of medication dosing error, the sponsor should be notified **immediately and under no circumstance should this exceed 24 hours**.

Dosing errors are reportable irrespective of the presence of an associated AE, including:

- Medication/dosing errors involving subject exposure to any of the study products;
- Potential medication/dosing errors or uses outside of what is foreseen in the protocol that do or do not involve the participating subject.

If a dosing error is accompanied by an AE, as determined by the investigator, the dosing error and, any associated adverse event(s) are to be captured in the CRF AE form.

6.2.2 Overdose

An overdose is a deliberate or inadvertent administration of a product at an amount higher than specified in the protocol.

Overdose is not likely to occur in this study.

Limited quantities of the study product(s) will be supplied, and closely monitored by the site for each subject.

Overdose per se is not an AE. However, any clinical sequelae of an overdose should be reported as an AE (and serious adverse event (SAE), if appropriate). For reporting, follow the AE and SAE reporting instructions.

6.3 Investigational/Study Product Storage

The investigator or designee must confirm appropriate temperature conditions have been maintained during transit for all study products received and any discrepancies are reported and resolved before use according to the supplied shipping documentation.

The investigator, or designee, will ensure that all study products are stored in a secured area with controlled access under required storage conditions and in accordance with applicable regulatory requirements and the product label.

Site systems must be capable of measuring and documenting (for example, via a log), at a minimum, daily minimum and maximum temperatures for all site storage locations (as applicable, including frozen, refrigerated, and/or room-temperature products). This should be captured from the time of first product receipt throughout the study. Even for continuous monitoring systems, a log or site procedure that ensures active daily evaluation for excursions should be available. The operation of the temperature-monitoring device and storage unit (for example, refrigerator), as applicable, should be regularly inspected to ensure it is maintained in working order.

Any excursions from the product-label storage conditions should be reported to appropriate site staff upon discovery and communicated to sponsor as soon as possible. The site should actively pursue options for returning the product to the storage conditions as described in the labeling, as soon as possible. Excursions from the storage requirements, including any actions taken, must be documented as a protocol deviation and reported to the Sponsor.

Once an excursion is identified, the affected product (or products) must be quarantined and not used until the sponsor provides documentation of permission to use. Use of any of the affected product(s) prior to sponsor approval will be considered a protocol deviation.

Site staff will instruct subjects on the proper storage requirements for all take-home products, as per the labels.

6.4 Investigational/Study Product Accountability

All products supplied are for use only in this clinical study and should not be used for any other purpose.

All study products must be received by a designated person at the study sites, handled and stored safely and properly, and kept in a secured location to which only the staff have access. Upon receipt, all study products should be stored according to the instructions specified on the product labels. Study products are to be dispensed only to subjects enrolled in the study in accordance with the protocol, by authorized site staff.

The investigative site must maintain adequate records documenting the receipt, use, loss, or other disposition of all the product supplies. All study products will be accounted for using the investigational/study product accountability form/record. The investigator is responsible for study product accountability, reconciliation, and record maintenance.

The accountability records must be available for inspection by the study monitor during the study. Monitoring of product accountability will be performed by the monitor during site visits and at the completion of the study.

Subjects should return all products to the study site

6.4.1 Destruction of Investigational/Study Product Supplies

At the end of the study, the Principal Investigator or an appropriate designee, and a representative of GSK CH (study monitor) will inventory all used and unused study products and sundry items. The study product accountability record for returned study products will then be completed. All study product (used and unused) for this clinical study (including empty containers), will be returned for destruction to the GSK CH Clinical Supplies Department or designated vendor using the return instructions provided. Detailed instructions for the return of study product for the accountability checks and subsequent destruction will be provided by GSK CH during the study in time for study close out visit.

6.5 Blinding and Allocation/Randomization

All subjects will be centrally randomized to one of the 3 study arms using an Interactive Response Technology (IRT). Before the study is initiated, training, login information and directions for the IRT will be provided to the site. Study products will be dispensed according to the instruction received through the IRT at the appropriate study visit.

The Sponsor will provide 2 randomization schedules; one will be a randomization schedule for the allocation of study product to subject, and a second one for the LAST allocation per [Lactic Acid Stinging Test \(LAST\)](#), for the left and right side of the nasolabial fold, to ensure a balanced randomization of the two solutions (lactic acid and saline solution) for the screened subjects.

Subjects will be randomized into the study and receive product provided they have satisfied all subject selection criteria.

Returned study products should not be re-dispensed to any subject.

The investigator's knowledge of the product allocation should not influence the decision to enroll a subject or affect the order in which subjects are enrolled.

This study is described as examiner-blind (the clinical examiners (dermatologist, ophthalmologist) will be blinded to the product the subject received).

To ensure the examiner remains blinded throughout the study, staff involved in the dispensing of study products will work in a separate area. The examiner is not permitted in any area where study product is stored, dispensed, or in use.

Subjects will be instructed not to remove study products outside of the dispensing room, while at the study site. Dispensing staff will not be involved in any safety assessment procedures during the study.

6.6 Breaking the Blind

At the initiation of the study, the study site will be instructed on the method for breaking the blind. The method will be an electronic process.

The electronic system will be programmed with blind-breaking instructions. In case of an emergency, the investigator has the sole responsibility for determining if unblinding of a subject's product assignment is warranted. Subject safety must always be the first consideration in making such a determination. If the investigator decides that unblinding is warranted, the investigator should make every effort to contact the sponsor prior to unblinding a subject's product assignment unless this could delay emergency treatment of the subject.

If a subject's product assignment is unblinded, the sponsor must be notified within 24 hours after breaking the blind. The date and reason that the blind was broken must be recorded in the source documentation and case report form, as applicable.

Any AE associated with breaking the blind must be recorded and reported as specified in this protocol. The study site may also be required to inform the EC if the blind is broken.

6.7 Compliance

Study products will be applied under the supervision of investigator site personnel for the first application at the study site.

A paper diary will be supplied to promote compliance and to capture details of product use throughout the study period. Subjects may also record additional information such as AEs or medications used during the home use period in the provided diary. Any additional details relevant to safety that have been captured in the paper diary should be reviewed by the investigator (or suitably qualified designee) with the subjects and transcribed to the CRF (in English) as appropriate.

The number of any missed or additional applications will be captured as protocol deviations and transcribed from the diary into the CRF. Subjects will be instructed in the correct usage requirements and diary completion post randomization at the first supervised product application.

6.8 Concomitant Medication/Treatment(s)

Any medications, treatments or vaccinations (including over-the-counter or prescription medicines, vitamins, and/or herbal supplements) taken during the study, from signing the informed consent, must be recorded in the CRF with indication, reason for use, unit dose, daily dose, and start and stop dates of administration. All subjects will be questioned about medications and treatments at each site visit.

Medication/treatments taken within 30 days of signing the informed consent form will be documented as a prior medication/treatment. Medications/treatments taken after the first supervised test product application (serum, lotion or cream) will be documented as concomitant medication/treatments.

7 DISCONTINUATION OF STUDY INTERVENTION AND SUBJECT DISCONTINUATION/WITHDRAWAL

7.1 Subject Discontinuation/Withdrawal

A subject may withdraw from the study at any time at his or her own request or may be withdrawn at any time at the discretion of the investigator or sponsor for safety, behavioral reasons, or the inability of the subject to comply with the protocol-required schedule of study visits or procedures.

The following circumstances require discontinuation of study product and/or premature subject withdrawal:

- Protocol violation that may impact the subject's safety
- Withdrawal of informed consent
- Subject lost to follow-up
- Unblinding of the subject
- Pregnancy

If a subject is discontinued or prematurely withdraws from the study, the reason(s) for discontinuation or withdrawal and the associated date must be documented in the relevant section(s) of the CRF.

7.2 Lost to Follow up

If a subject fails to return to the site for a required study visit the site must attempt to contact the subject and reschedule the missed visit as soon as possible and counsel the subject on the importance of maintaining the assigned visit schedule and ascertain whether the subject wishes to and/or should continue in the study.

A subject will be considered lost to follow up if he or she repeatedly fails to return for scheduled visits and is unable to be contacted by the study site. Before a subject is deemed lost to follow up, the investigator or designee must make every effort to regain contact with the subject (where possible, 3 telephone calls and, if necessary, a certified letter to the subject's last known mailing address or local equivalent methods). These contact attempts should be documented. If contact is made with the subject, the investigator should inquire about the reason for withdrawal, request that the subject return all products that they had been dispensed and if appropriate request that the subject return for a final visit and follow-up with the subject regarding any unresolved adverse events (AEs).

Final safety assessments may be carried out when the subject returns to the study site, at the investigator's discretion, which could include the following:

- Dermatologist assessment of cutaneous irritation
- Ophthalmologist assessment of ocular irritation
- Subject self-assessment questions

Should the subject continue to be unreachable, he/she will be considered to have withdrawn from the study and lost to follow up.

Lack of completion of all or any of the early termination procedures will not be viewed as protocol deviations so long as the subject's safety was preserved.

If the subject withdraws from the study and withdraws consent for disclosure of future information, no further evaluations should be performed, and no additional data should be collected. The sponsor may retain and continue to use any data collected before such withdrawal of consent.

8 STUDY PROCEDURES

This section lists the procedures to be completed at each planned study visit. The timing of each procedure is listed in the [Schedule of Activities](#).

Adherence to the study design requirements, including all procedures are essential and required for study conduct.

8.1 Visit 1 (Day -6 to 0) Screening

Screening procedures will be conducted by the Investigator, or suitably qualified designees.

The following procedures will be completed:

8.1.1 Informed Consent

The investigator, or designee, must obtain informed consent from each subject participating in this study after adequate explanation of the aims, methods, objectives, and potential hazards of the study. Two copies of the informed consent form (ICF) will be signed and dated by the subject, the subject will retain one copy and the other will be kept at site.

The investigator, or designee, must also explain to the subjects that they are completely free to refuse to enter the study or to withdraw from it at any time. Appropriate forms for documenting a signed and dated consent will be provided by either the investigator or by GSK CH.

The investigator, or designee, should sign and date each copy of the ICF to confirm that the consent process was completed correctly after the subject has signed.

The time the subject signed the informed consent form will also be documented as this is the point at which all AE's will be captured from. The date and time of consent will be transcribed to the CRF.

If, during a subject's participation in the study, any new information becomes available that may affect the subject's willingness to participate in the study, each ongoing subject should receive a copy of this new information and be re-consented into the study. Each subject should be provided with a copy of the signed and dated amended consent form. The date of re-consent will be recorded on the CRF.

After signing the ICF, subjects will undergo the screening assessments to confirm that they meet the inclusion criteria and none of the exclusion criteria. If the subject is confirmed eligible by the investigator (or designee) to participate in the study the subject is considered enrolled in the study.

8.1.2 Demographics

The following demographic information will be recorded in the CRF: year of birth and race. Fitzpatrick skin type assessment [APPENDIX 2 – FITZPATRICK SKIN TYPE GRADING](#) will also be captured. The Fitzpatrick skin type scale is a numerical classification that is widely used by dermatologists to classify a person's skin type by their response to sun exposure (Fitzpatrick, 1988). The classification of a subject's Fitzpatrick skin type will be conducted by a trained evaluator.

Race of subjects will be recorded in accordance with FDA Guidance for Industry: Collection of Race and Ethnicity Data in Clinical Trials, 2005.

8.1.3 Medical History Current and Prior Medication/Treatment

Details of relevant medical and surgical history (in the last year), including allergies or drug sensitivity, will be documented in the CRF.

Prior medications/treatments, including prescription and non-prescription drugs, dietary supplements and herbal remedies, taken in the last 30 days and prior to first product application, will be documented in the CRF.

8.1.4 Inclusion/Exclusion Criteria

Review of inclusion and exclusion criteria as appropriate for the visit and information will be documented in the CRF.

[figure not shown]
8.1.5 Lactic Acid Stinging Test (LAST)

Subjects will be instructed to wash their face with room-temperature tap water and to pat dry with paper towels provided by the investigational site. This will ensure a clean surface with which to conduct the LAST.

Approximately 30 minutes after washing, a trained technician will apply an aqueous solution of 10% lactic acid to one nasolabial fold and a saline solution (0.9 Molar) to the other nasolabial fold in the following manner:

The test substances (10% lactic acid; 0.9M NaCl) will be applied concurrently to either the right or the left nasolabial fold. The Sponsor will provide a randomization schedule for the left and right side of the face to have a balanced randomization of the two solutions for the screened subjects.

- A separate swab will be dipped into each test solution (lactic acid and saline solution)
- Each swab will be applied to the upper end of the nasolabial fold and moved in a circular area across the infraorbital part of the cheek under the outer corner of the eye and back along the fold of the nostrils, and along the nasolabial fold to the side of the corner of the mouth, ending at the point where the application started. (See Figure 8-1 as an example).

Figure 8-1

- The complete movement will be repeated once more.
- The applied test substances should not extend beyond this area.
- For each subject, fresh swabs will be used.

Subjects will be asked to report any sensations of discomfort 2-3 minutes and 5-6 minutes after application of the solutions on a 4-point scale (Christensen and Kligman, 1996) per [Table 8-1](#). Scores will be entered into the CRF by a technician.

The test will be suspended after 6 minutes if no local sensation is reported, or immediately upon any reported score of 3. The subjects will be instructed to remove the solutions by thoroughly washing with room-temperature tap water and drying their face with a paper towel.

The sum of the 2-3 and 5-6-minute subject self-assessment scores will be calculated in the CRF for the lactic acid and saline-treated nasolabial folds.

Subjects who report a total score ≥ 2 for the lactic acid-treated site compared to the saline-treated site will be considered to have had a positive response to the LAST. Otherwise, subjects will be considered to have had a negative response to the LAST. Only subjects with a positive response to the LAST will be enrolled into the study.

Table 8-1 Lactic Acid Sting Test Score

Score	Description
0	No discomfort/sensation
1	Mild discomfort/stinging
2	Moderate discomfort/stinging
3	Severe discomfort/stinging

Sensations of discomfort may or may not appear. In instances where sensations of discomfort do appear, they may go unnoticed for 1-2 minutes at the start but should intensify up to 5-6 minutes.

Any observed response that can be denoted according to the score of the reactions (per [Table 8-1](#)) will not be considered an adverse event. Only in the case of unusual reactions, in the

opinion of the qualified dermatologist, will these reactions and the consequences observed upon evaluation be documented as AE's.

The subject will not be informed which nasolabial fold received the lactic acid solution and which nasolabial fold received saline solution.

If Visit 2 is combined with Visit 1, the dermatologist and ophthalmologist assessments and the subject self-assessments will be conducted prior to the LAST. Eligible subjects will not apply study product until at least 30 minutes following the end of the LAST.

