Sensitive skin may be characterized by sensations including stinging, burning and itching, often without any visible signs or symptoms. The absence of visible signs or symptoms of irritation presents a challenge in the diagnosis of sensitive skin. However, several substances are known to trigger an irritant response in people with sensitive skin, such as benzoic acid, cinnamic acid, non-ionic emulsifiers, sodium lauryl sulfate, lactic acid, propylene glycol, urea and sorbic acid (De Groot *et al*, 2010; Lundov *et al*, 2010). Therefore, a routine test to diagnose sensitive skin is a lactic acid sting test (LAST), whereby an aqueous solution of lactic acid is applied to the facial nasolabial fold to try and trigger a sensorial response, often alongside a placebo such as saline. The stinging sensation response to the irritant may be measured in a binary way (i.e. presence or absence) or with a magnitude scale (Farage *et al*, 2006). The LAST procedure allows for the characterization and enrollment of subjects with sensitive facial skin into clinical trials to enable the local tolerance of an investigational product to be investigated in this population.

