5.2 Inclusion Criteria

An individual must meet all the following inclusion criteria to be eligible for enrollment into the study:

1. Subject provision of a signed and dated informed consent document indicating that the subject has been informed of all pertinent aspects of the study before any assessment is performed.
2. Subject is female who, at the time of screening, is between the ages of 18 and 65 years, inclusive.
3. A subject who is willing and able to comply with scheduled visits, the application schedule, the lifestyle guidelines, and other study procedures.
4. A subject in good general and mental health with, in the opinion of the investigator or medically qualified designee (if the investigator is not suitably qualified), no clinically significant/relevant abnormalities in medical history or upon dermatologist and ophthalmologist examination, or condition, that would impact the subject's safety, wellbeing or the outcome of the study, if they were to participate in the study, or affect the individual's ability to understand and follow study procedures and requirements.
5. Subjects with sensitive facial skin, defined as a positive response to a LAST in the nasolabial area.
6. A subject with a dermatologist signs and symptoms of cutaneous irritation score of 0.5 (very slight) or greater for erythema. Per [Table 9-1 Dermatological Evaluation](#)
7. A subject with a dermatologist signs and symptoms of cutaneous irritation score of 0.5 (very slight) or greater for dryness. Per [Table 9-1 Dermatological Evaluation](#)
8. A subject with a dermatologist signs and symptoms of cutaneous irritation score of 0 (none) or 0.5 (very slight) for scaling. Per [Table 9-1 Dermatological Evaluation](#)
9. A subject with a dermatologist signs and symptoms of cutaneous irritation score of 0 (none) or 0.5 (very slight) for edema. Per [Table 9-1 Dermatological Evaluation](#)

10. A subject with an ophthalmologist total signs and symptoms of ocular irritation score of zero (0). Per [Table 9-2 Ophthalmological Evaluation](#)

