6.1 Investigational/Study Product Supplies

The following study products will be supplied by the Clinical Supplies Department, GSK CH:

Table 6-1 Investigational/Study Product Supplies

	Investigational Product 1	Investigational Product 2	Investigational Product 3
Product Name	Developmental Serum	Developmental Lotion	Developmental Cream
Product Formulation Code (MFC)	CCI [REDACTED]	CCI [REDACTED]	CCI [REDACTED]
Product Format	40 mL pump pack	50 mL tube	50 mL tube
Dispensing Details	A kit will be dispensed to each subject containing 2 bottles/tubes		
Application Quantity	To be used as per normal home use application in place of the current facial skin care product.		
Route of Administration	Topical dermal (facial) application		
Application Instructions	Apply twice daily to freshly cleansed skin, continue with your normal moisturising	Apply twice daily to freshly cleansed skin.	Apply twice daily to freshly cleansed skin.

Property of GSK Consumer Healthcare - Confidential

May not be used, divulged, published or otherwise disclosed without the consent of GSKCH

SOP-208661 Clinical Protocol Template v5.0

Page 23 of 56

	routine.		
Return Requirements	All used/unused samples to be returned to the study site		

The contents of the label will be in accordance with all applicable regulatory requirements and will be the responsibility of the Clinical Supplies Department, GSKCH.

Opaque bags will be supplied by the Clinical Supplies Department, GSKCH for dispensing of the kits to subjects.

Other items to be supplied by the clinical investigational site:

- Aqueous Lactic Acid solution (10%) – For LAST
- Saline solution (0.9 Molar) – For LAST
- Cotton tipped swabs - For LAST
- Paper towels

Supplies provided by the clinical investigational site must also be stored in compliance with the label requirements in a secure place with limited or controlled access.

Detailed instructions for the return of study product/study supplies for the accountability checks and subsequent destruction which will be provided by GSK CH during the study in time for study close out visit.

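### The LAST control is specified as 0.9 Molar saline, 5.8 times the strength of 0.9% w/v saline, with no rationale, although its score feeds the test that decides entry

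*Protocol*

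**What the plan says.** Protocol 8.1.5 applies lactic acid to one side of the face and "a saline solution (0.9 Molar) to the other nasolabial fold". It then repeats the strength with the salt named: "The test substances (10% lactic acid; 0.9M NaCl) will be applied concurrently to either the right or the left nasolabial fold". The supply lists in Protocol 6.1 and SAP 1.3 also give 0.9 Molar and make the site responsible for providing the solution. Appendix 1 of the protocol defines M as Molar. No section gives any other strength or explains this one.

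Protocol 2.2, introducing the test, says that lactic acid is applied "often alongside a placebo such as saline".

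The subject scores each side from 0 to 3 at 2-3 minutes and again at 5-6 minutes, and the two scores are summed for each side. The rule for a positive result is: "Subjects who report a total score ≥ 2 for the lactic acid-treated site compared to the saline-treated site". The test ends at 6 minutes if nothing is felt, "or immediately upon any reported score of 3"; the side is not specified. The result decides entry: "Only subjects with a positive response to the LAST will be enrolled into the study". Inclusion criterion 5 (Protocol 5.2) reads: "Subjects with sensitive facial skin, defined as a positive response to a LAST in the nasolabial area". Under Protocol 5.6, screen failures are not screened again.

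**The concern.** A control for a sting test is useful if it causes little sensation of its own, so that the lactic acid score can be read against it. As written, the control is a strongly hypertonic salt solution. The digits 0.9 are those of 0.9% w/v saline, which is why a unit slip comes to mind. Because the site makes up or buys the solution itself, the written strength is the working instruction.

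What is at stake is the definition of the study population. The LAST alone decides who counts as having sensitive facial skin, and every tolerance objective is stated for that group. If the control itself stings and its score is set against the lactic acid score, a woman can fail the test because of the control, and that decision is final.

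**Working it through.** **Inputs.** Saline strength 0.9 mol/L (Protocol 6.1 and 8.1.5, SAP 1.3). Scores 0 to 3 at two times, so each side totals 0 to 6 (Protocol 8.1.5 and Table 8-1). Completers 45 per arm and assumed event rate 4% (Protocol 12.1, SAP 1.4). The molar mass of NaCl, 58.44 g/mol, is a physical constant that the documents do not give.

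**1. The plan's own probabilities.** Fewer than 10% events among 45 subjects means at most 4. For a binomial with n = 45 and p = 0.04, P(X ≤ 4) = 0.9668, and 0.9668³ = 0.9037. Both stated figures reproduce. Saline strength does not enter them.

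**2. Unit conversion.**
- 0.9 mol/L × 58.44 g/mol = 52.6 g/L = 5.26% w/v.
- 0.9% w/v = 9 g/L, and 9 / 58.44 = 0.154 mol/L.
- Ratio: 52.6 / 9 = 5.84.
- Ideal osmolarity (two ions per formula unit): 2 × 900 = 1800 mOsm/L, against 2 × 154 = 308 mOsm/L.

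**3. Effect on the LAST result, difference reading.** Suppose positive means lactic acid total minus saline total of 2 or more.

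| Saline total | Lactic acid total needed | Totals that pass at saline 0 but now fail |
|---|---|---|
| 0 | 2 | none |
| 1 | 3 | 2 |
| 2 | 4 | 2, 3 |
| 3 | 5 | 2 to 4 |
| 4 | 6 | 2 to 5 |
| 5 or 6 | cannot be met | 2 to 6 |

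Mild stinging on the control at both times (1 + 1 = 2) moves the requirement from 2 to 4. On this reading, control stinging can only turn positives into negatives, never the reverse.

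**4. Effect on the LAST result, absolute reading.** If positive means a lactic acid total of 2 or more whatever the saline side scores, the saline total changes nothing.

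**5. Early stop.** A control score of 3 at 2-3 minutes appears to end the test, so no 5-6 minute score would exist for either side. The protocol does not say how the total is then formed. If only the available scores are used, the difference is at most 3 − 3 = 0 and the woman is negative under the difference reading.

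**The case against.** The strongest reply is that the documents agree with one another on the number. Every mention of the strength is 0.9 Molar, and no section says 0.9% or physiological. Protocol 2.2 describes the LAST in general, not this study's control, and sets no strength for a placebo saline. No calculation in the plan fails. This stands: the point concerns an unexplained specification that fits poorly with a described role. It is not a numerical contradiction, and it would be too strong to say that 0.9% w/v was certainly intended.

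Second, nothing in the documents shows that 0.9 M saline stings during a six-minute swab test. This also stands. That it can sting is an inference from its strength.

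Third, the effect on classification needs the difference reading, and the rule does not state a subtraction outright. The difference reading is the more natural one, since otherwise the saline total is calculated and compared to no purpose, but the wording leaves it open.

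Fourth, a reader might infer that the more reactive women are lost and that this favours the conclusion of 10% or fewer intolerant subjects. The documents do not support that. At a control total of 2, the women lost have lactic acid totals of 2 or 3 and those with 4 to 6 still pass, so the test becomes stricter on lactic acid response. Women who sting to saline may be more reactive in general, which pulls the other way. In addition, the primary endpoint is the dermatologist's visual grading of erythema, dryness, scaling and edema, not stinging, and Protocol 2.2 notes that sensitive skin often shows no visible signs.

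What survives is that the site is told to use a solution of this strength, no reason is given, and its score is part of the comparison that decides entry.

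**Conclusion.** The point holds as a should-fix specification issue. The control as written is 5.26% w/v NaCl, 5.8 times 0.9% w/v saline; this rests only on the molar mass of NaCl. It fits poorly with the placebo role described in Protocol 2.2. A slip of Molar for % w/v is plausible but unconfirmed.

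The consequence is conditional on two assumptions: that the solution causes some stinging, and that positivity is a difference between sides. If both hold, each control point adds one to the lactic acid total needed, and some women could be wrongly classed as LAST negative with no second screening.

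The number affected and the direction of any shift in skin reactivity cannot be determined from the documents. A reader might also infer a heavier screening load than the roughly 350 planned, but no loss rate is available from which to project one. The LAST precedes randomization, so balance between arms is unaffected, as are the 96.68% and 90.4% probabilities.

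**What to change.** Before the first LAST, the sponsor should reconcile the specified strength with the placebo role.

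- If an inert control was intended, correct the units consistently in Protocol 6.1, Protocol 8.1.5 and SAP 1.3 (the likely slip being Molar for % w/v), and tell the site which solution to use.
- If 0.9 M was intended, state the reason in Protocol 8.1.5.

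The cost is a wording change in the protocol and the SAP and one message to the site. No procedure, visit or subject is added. Timing matters because a woman already screened out cannot be re-screened under Protocol 5.6.
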